## 9.6 Data Management

### 9.6.1 Statistical analysis

Statistical analyses will be performed using statistical packages (Statistical Analysis System [SAS], STATA and R [version 3.1.1, or above]) and will be described in detail in the Statistical Analysis Plan (SAP).

### 9.6.2 Database management

The processes for database management differ by country. Generally, the data is stored at the database level and analysed in accordance with local policy. SAS or R language (version 3.1.1, or above) will be utilized for access to the raw data, to manage the analytic datasets and to conduct data analysis. If the study is conducted by a third party, the datasets and analytic programs will be stored according to the vendor's procedures. This study will follow the relevant chapters of the European Network of Centres for Pharmacoepidemiology and Pharmacovigilance (ENCePP) and the International Conference on Harmonisation (ICH) guidelines for data management.

## 9.7 Data Analyses

### 9.7.1 General considerations

The distribution of each variable will be examined graphically using boxplots, symmetry plots, normal quantile plots and normal probability plots. Exploratory analyses to provide insight into general patterns will be conducted using number and percent within each category for categorical variables, and mean (standard deviation, SD), median (interquartile range, IQR), and other relevant summary statistics for continuous variables. Where appropriate, a log transformation of continuous variables will be applied to handle skewness (back-transformed prior to reporting) or a non-parametric approach will be adopted if there is no appropriate transformation. Quantitative variables may be categorised into quartiles as required. To identify outlying values of variables, such as gestational age and weight, the Cook's distance will be calculated for each offspring after model fitting. The Cook's distance measures the change in fitted values with and without the presence of each offspring, i.e. the impact of each offspring on the fitted values. Offspring that have a Cook's distance greater than four times the mean will be classified as influential. For influential offspring it is likely that variables had extreme values. If extreme values (outliers or leverage points) are observed, they will be assumed as missing and excluded from the final model.

The descriptive (section 9.7.2), and comparative (section 9.7.3.2) analyses will be undertaken by country. For analysis of the primary outcome, data will then be pooled across the three countries, via a meta-analytic approach (see section 9.7.6). For analysis of the secondary outcome, data will be pooled across Norway and Denmark only via a meta-analytic approach

---

 A data point is influential if it unduly influences any part of a regression analysis, such as the predicted responses, the estimated slope coefficients, or the hypothesis test results.

 Outliers and high leverage data points have the potential to be influential, but generally further investigations are needed to determine whether or not they are actually influential.

(see section 9.7.6). In addition, the case assessment will also be presented by country (see section 9.3.2.3). Table 7 shows the analyses presented in Section 9.7 by study outcome.

The populations at study will include each individual offspring (or non-live birth) as the unit for analysis, therefore if the mother and father have more than one offspring they can be included more than once in the study; each offspring/non-live birth will coincide with the linked triple offspring/non-live birth, mother and father. Furthermore all variables collected for fathers and mothers will be re-calculated for each pregnancy.

**Table 7: Analyses for study objectives, by Data Analysis section**

Sub-section		Cohort	
Section number	Analysis description	NDD	CM
9.7.2.1	Cohort characteristics	x	x
9.7.2.2	Cumulative incidence proportion, rate and time to event	x	x 
9.7.3.1	Univariate Analyses	x	x
9.7.3.2.1	Effect estimation - NDD, including ASD	x	
9.7.3.2.2	Effect estimation – CM		x
9.7.3.2.3	Propensity score	x	x
9.7.6	Meta-analysis	x	x
9.7.4	Exploratory objective analyses	x	x
9.7.5	Sensitivity analyses	x	x
9.7.6	Missing data analysis	x	x

NDD: Neurodevelopmental Disorders; ASD: Autism Spectrum Disorder; CM: Congenital Malformations  
 1 - for CM only cumulative incidence proportion will be calculated.

## 9.7.2 Descriptive Analyses

### 9.7.2.1 Cohort characteristics

Demographic characteristics of mother, father and offspring will be presented for both *the primary and secondary outcome cohort* and separately for *paternal exposure groups* (valproate and lamotrigine/levetiracetam (composite and separately) in monotherapy). Other characteristics (e.g. age at first diagnosis of outcome) and other co-existing risk factors for primary and secondary outcomes of interest (e.g. medication use within 3 months prior to LMP2 (paternal and maternal) and during pregnancy (maternal)), and concurrent relevant morbidities according to each relevant index date, will also be summarised. Thus, contingency tables reporting the characteristics of offspring with NDD, including ASD, as well as outcomes of CM occurrence by paternal and maternal exposure groups, will be provided. Summary description of the frequency of extremely low birth weight, very preterm and extremely preterm newborns will be provided for the primary outcome cohort, by paternal and maternal exposure group (a sensitivity analysis will be performed excluding preterm and low birth weight offspring, section 9.7.5). Summary description of the frequency of children exposed to AEDs

and/or diagnosed with epilepsy after birth will be provided (a sensitivity analysis will be performed including those children, section 9.7.5). Summary description of the frequency of stillbirth, spontaneous abortion, intrauterine growth retardation and perinatal mortality, associated to a diagnosis of CM, will be also provided. Data will also be stratified by age and calendar period. A descriptive table of the frequency of fathers who switch to or switch from an AED other than valproate, lamotrigine or levetiracetam, even if on monotherapy, will be provided. A descriptive table with a summary of the case assessments (see section 9.3.2.3), undertaken by study clinical investigators using the registry data on a random sample of cases, will be provided at aggregate level.

A STROBE (STrengthening the Reporting of OBservational studies in Epidemiology) diagram will be provided to show exclusions to be applied in order to create cohorts for analysis.

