**Table 21: Intrauterine Growth Restriction- IGR**

ICD 10	Clinical Code Description
O36.5	Maternal care for poor foetal growth
P05.0	Light for gestational age
P05.1	Small for gestational age
P05.9	Slow foetal growth, unspecified
P07.0	Extremely low birth weight
P07.1	Other low birth weight

ICD-10: International Statistical Classification of Diseases and Related Health Problems 10th Revision.

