**Table 22: Perinatal mortality**

ICD 10	Clinical Code Description
P95	Still birth
Z371	Single Stillbirth
Z37.3	Twins, one liveborn and one stillborn
Z37.4	Twins, both stillborn
Z37.7	Other multiple births, all stillborn
Z37.6	Other multiple births, some liveborn

ICD-10: International Statistical Classification of Diseases and Related Health Problems 10th Revision.

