**Table 26: Stillbirth**

ICD 10	Clinical Code Description
P95	Still birth
Z371	Single Stillbirth
Z37.3	Twins, one liveborn and one stillborn
Z37.4	Twins, both stillborn
Z37.7	Other multiple births, all stillborn
O312	Continuing pregnancy after intrauterine death one foetus or more
O36.4	Maternal care for intrauterine death
Z37.6	Other multiple births, some liveborn

ICD-10: International Statistical Classification of Diseases and Related Health Problems 10th Revision.

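### As coded, perinatal mortality is a strict subset of stillbirth with no death after live birth, and the growth-restriction list also counts low birth weight regardless of gestational age

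*Protocol*

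**What the plan says.** Section 9.7.2.1 of the protocol commits to describing the "frequency of stillbirth, spontaneous abortion, intrauterine growth retardation and perinatal mortality, associated to a diagnosis of CM". Stillbirth and perinatal mortality are named as separate items, and both are limited to cases with a malformation diagnosis.

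The section does not cite code lists by number, but Annex 3G has exactly one list under each name:

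- "Table 22: Perinatal mortality": P95, Z371, Z37.3, Z37.4, Z37.7, Z37.6.
- "Table 26: Stillbirth": the same six codes plus O312 and O36.4 (the latter labelled "Maternal care for intrauterine death").
- "Table 21: Intrauterine Growth Restriction- IGR": O36.5, P05.0, P05.1 and P05.9, plus P07.0 ("Extremely low birth weight") and P07.1 ("Other low birth weight").

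No other place in the protocol defines perinatal mortality or growth restriction. Table 5 lists registers holding vital status in all three countries, and Medical Birth Registries holding birth weight and gestational age, but nothing ties them to these two items.

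**The concern.** Perinatal mortality is ordinarily stillbirth plus death in the first days of life. A list that draws only on stillbirth codes adds nothing to the stillbirth row printed beside it, and it leaves out the part that makes the term different: the live-born child with a malformation who dies soon after birth. A reader of the report would take the row at its name and could draw false reassurance from it. This matters most in Sweden, where exploratory objective 7 repeats the descriptive analyses in live births only and the row would show no deaths whatever happened.

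The growth-restriction list has a lesser fault of the same kind. Birth weight below a threshold is not growth restriction unless gestational age is taken into account, so the row mixes two things under one label.

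The lists are fixed in the protocol annex, so programming them exactly as written produces mislabelled rows.

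**Working it through.** The plan states no figure here, so the check is a comparison of the annex lists as sets, with the dots in the codes ignored.

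**Perinatal mortality against stillbirth**

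| Code | Table 22 | Table 26 | Table 53 (multiple pregnancy) |
|---|---|---|---|
| P95 | yes | yes | no |
| Z371 | yes | yes | no |
| Z37.3 | yes | yes | yes |
| Z37.4 | yes | yes | yes |
| Z37.6 | yes | yes | yes |
| Z37.7 | yes | yes | yes |
| O312 | no | yes | under O31 |
| O36.4 | no | yes | no |

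1. Six of six Table 22 codes are in Table 26, which has two more. Table 22 is a strict subset, so in any group the perinatal mortality count is at most the stillbirth count.
2. Table 22 shares no code with Table 23 (live birth), and it carries no neonatal-death code and no vital-status rule. The one label that does not mention stillbirth is Z37.6 ("Other multiple births, some liveborn"). Table 26 lists that code as stillbirth as well.
3. Section 9.2.2 admits singletons only. Four of the six Table 22 codes are multiple-birth codes, so only 6 − 4 = 2 can act: P95 and Z371. The stillbirth row keeps those two and O36.4. A singleton coded only O36.4 is a stillbirth but not a perinatal death, so the perinatal row can fall below the stillbirth row. No definition that includes all stillbirths allows that.
4. Sweden's malformation cohort holds live births only (sections 9.1 and 9.2.2). Neither of the two remaining codes can describe a live-born singleton, so the row is empty there by construction.

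**Size of the shortfall.** The protocol gives no early neonatal death rate. Write S for stillbirths, E for early neonatal deaths and s = E/(S + E). The row reports at most S, which is a fraction 1 − s of perinatal deaths. If s is between 20% and 50% (an assumption, not a document figure), at most 80% to 50% of perinatal deaths appear.

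**Growth restriction.** Of the six Table 21 codes, four (O36.5, P05.0, P05.1, P05.9) concern fetal growth or size for gestation. The other two (P07.0, P07.1) concern birth weight alone, and no gestational-age condition is attached. An infant who weighs little only because of early birth is counted.

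**Scale of the rows.** Section 9.5 projects about 860 valproate-exposed offspring in Norway and 790 in Denmark for the malformation analysis, and cites 37.1 major malformations per 1000. That gives (860 + 790) × 0.0371 = 1650 × 0.0371 ≈ 61 offspring with a major malformation. The rows cover all malformations, so the true base is larger, but it remains a small group. If 2.5% of these 61 entered Table 21 through P07 alone (an assumption), that is 61 × 0.025 ≈ 1.5 children. At five times that share it is about 8.

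**The case against.** The strongest reply is that little depends on these rows. Neither item appears in any objective, in the risk-factor or confounder tables (Tables 2 to 4), or in any effect model. Section 9.7.2.1 gives them one sentence of summary description, and that sentence does not itself call for a split by exposure group. The split has to be inferred from the opening of the section and from the abstract. In Denmark, results on fewer than five cases are withheld (section 9.9.1). With about 790 × 0.0371 ≈ 29 major-malformation offspring in the valproate group, about 5/29 ≈ 17% would have to die before such a row could be released. All of this stands and sets the severity.

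It also rules out some stronger readings:

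- A reader might infer that a live-born malformed child who dies on day 1 drops out of the study. That is not so. Under section 9.3.2.2 a coded malformation in a live birth is a case of the secondary outcome, and death is a stated exit event. The child is missing from the mortality row only.
- A reader might infer that the growth-restriction row is really a preterm-birth row. Four of its six codes are apt and none is labelled as prematurity. The list is too wide, not wrong throughout.
- A reader might scale the excess to all births. The rows are restricted to offspring with a malformation, so an all-births denominator does not apply.

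It can also be said that the empty Swedish row merely reflects a disclosed restriction to live births. That is fair for stillbirth and spontaneous abortion. It is not fair for perinatal mortality, because early deaths of live-born children can be observed there.

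None of this answers the core point: a row named perinatal mortality that sits inside the stillbirth row is mislabelled.

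**Conclusion.** The point holds as a minor error of definition, wrong as written. Table 22 is a strict subset of Table 26, and in a singleton cohort only two of its codes can act. The reported perinatal mortality therefore cannot exceed stillbirth, omits early neonatal deaths of malformed live births, and is empty in Sweden. Table 21 is over-inclusive through two of its six codes.

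The conclusion assumes that the annex lists bearing these names are the ones used for section 9.7.2.1; no others exist in the protocol. The subset finding does not depend on which cut-off in days is chosen for early neonatal death. The amount by which perinatal mortality is understated cannot be derived from the protocol.

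A reader might infer that safety findings on paternal valproate are biased. The documents do not support that. The hazard ratio for neurodevelopmental disorders, the odds ratio for malformations and the sample size do not use Tables 21 or 22, and the damage is limited to descriptive tables.

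**What to change.** - **Perinatal mortality.** Define it as stillbirth by Table 26 plus death of a live-born child within 7 days of birth. Take the deaths from the vital-status sources already listed in Table 5: the Cause of Death Register in Sweden, the Central Person Register or Cause of Death Register in Norway, and the Civil Registration System in Denmark. In the Swedish tables, label the row early neonatal death. If the sponsor prefers not to add deaths after birth, rename the row or drop it, since it duplicates part of stillbirth.
- **Growth restriction.** Remove P07.0 and P07.1 from Table 21, or count them only under a stated gestational-age condition. Gestational age and birth weight are in all three Medical Birth Registries.

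The cost is one code-list edit and a re-run descriptive table. The registers involved are already among the study's listed sources, and no effect estimate has to be repeated.

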#### 9.7.2.2 *Incidence examination*

The cumulative incidence proportion, rate and time to onset of NDD, including ASD will be calculated as well as cumulative incidence proportion for composite CM endpoint and specific CM target body system organ groups based on ICD-10 codes. These statistics will be presented for each overall cohort and separately for offspring *paternally exposed to valproate or lamotrigine/ levetiracetam (composite and separately) in monotherapy 3 months prior to LMP2*.

The cumulative incidence (risk) of the primary outcomes reported each year will be explored by estimating the cumulative incidence of incident reports (plus 95% CI). For purposes of this analysis the denominator is defined according to the population initially at risk at the beginning of the study, since the estimates are cumulative; that is live births for NDD, including ASD and live plus non-live births for CM. The numerator will comprise of counts of incident events as recorded during each year and summed to reflect the cumulative count for all years up to that point. The cumulative incidence proportion will be calculated according to the formula:

$$\left( \frac{\text{Total number of offspring paternally exposed with newly diagnosed outcome during each cumulative year of interest}}{\text{Population initially at risk}} \right) \times 100$$

For each exposure group, the numerator for each year will contain the number of offspring for whom the incident outcome has been recorded in that year and will exclude offspring who have had an outcome previously, within the study period. The denominator will include offspring within the numerator and also offspring who did not have an outcome recorded in the current year or preceding years (i.e. only the ‘at risk’ population will be considered).

The cumulative incidence rate of the primary outcome will be modelled using survival methods and expressed as number of cases per 1000 patients-years at risk (+95%CI). Data may also be stratified according to other relevant strong risk factors for events of interest (age, gender) and stratum-specific incidence rates examined.

For the time to event analysis of the primary outcome, a semi-parametric Proportional Hazards (PH) regression model will be derived to describe the time to event, which will be presented graphically. At least 10 cases will be required per event for crude estimates. A smoothed estimate of empirical hazard function will also be plotted using an epanechnikov kernel (bandwidth to be determined empirically from data). These will be used to describe how the baseline risk of an event changes over time.

In addition, cumulative incidence proportions for the entire period, 0-12 years for Denmark and Sweden and 0-10 years for Norway, will also be presented; this will be calculated as the

total number of offspring experiencing the outcome (NDD and CM, separately) during the entire follow-up (i.e. the sum of the number of events for the years 0 to 12 for Denmark and Sweden, and 0 to 10 for Norway) divided by the initial number of offspring included at the start of follow-up (i.e., population used in the analysis). Furthermore considering index date in the CM cohort will start before or on date of birth and that patients will be followed up until 12 years of age at maximum (10 years of age for Norway), there will be patients with a follow-up longer than 12 years (10 years for Norway), and therefore cumulative incidence proportion for the entire follow-up will include a longer period than 12 years for Denmark and Sweden (but shorter than 13 years). For Norway, the cumulative incidence proportion for the entire follow-up will include a longer period than 10 years, but shorter than 11 years.

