#### 9.3.2.1 Neurodevelopmental disorders, including ASD

The **index date** will be defined as the birth date of the offspring from which offspring will be observed for occurrence of the outcome of interest.

The **exit date/end of follow-up** will be defined as the end of the study period (31 December 2018 for Denmark and 31 December 2019 for Sweden and Norway), death, emigration (where available), reaching the age of 12 years for Denmark and Sweden and the age of 10 years for Norway or date of first diagnosis of the outcome at study, which-ever is the soonest.

The primary outcome is NDD including ASD, will be defined as a diagnosis of at least one the ICD-10 codes presented in codelist Table 10. Please note that ASD codelist is presented separately in the codelist Table 8, and NDD without ASD in the codelist Table 9.

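### Section 9.7.2.2 defines the yearly cumulative incidence proportion both as a cumulative risk and as a one-year risk among offspring still event-free

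*Protocol*

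**What the plan says.** Section 9.7.2.2 (Incidence examination) of the protocol describes the cumulative incidence proportion for each year, overall and by paternal exposure group. The denominators it names cover both the NDD and the CM cohorts.

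- **Before the formula (rule A).** The denominator is fixed: "the denominator is defined according to the population initially at risk at the beginning of the study, since the estimates are cumulative". The numerator is "counts of incident events as recorded during each year and summed to reflect the cumulative count for all years up to that point". The displayed formula also divides by the population initially at risk.
- **After the formula (rule B).** The numerator, set separately per drug, becomes a count for one year: "the numerator for each year will contain the number of offspring for whom the incident outcome has been recorded in that year". It also "will exclude offspring who have had an outcome previously, within the study period". The denominator changes too: "The denominator will include offspring within the numerator and also offspring who did not have an outcome recorded in the current year or preceding years".
- **End of the same section.** A separate proportion for the entire period (0-12 years in Denmark and Sweden, 0-10 years in Norway) is the sum of the yearly events "divided by the initial number of offspring included at the start of follow-up (i.e., population used in the analysis").

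Follow-up for NDD ends at the latest on "reaching the age of 12 years for Denmark and Sweden and the age of 10 years for Norway" (section 9.3.2.1).

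**The concern.** Rule A is the share of the starting cohort diagnosed by the end of year k. Rule B is the probability of a first diagnosis during year k among those who reached that year without one. These are different quantities, yet the section gives both the same label and no separate name for the second. A programmer can follow one paragraph only by breaking the other.

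What is at stake is the yearly absolute risk by drug. The abstract makes cumulative incidence part of the description of NDD risk and time to onset. The note to Table 7 (section 9.7.1) says that cumulative incidence proportion is the only incidence measure calculated for CM. A reader who takes a rule B figure for a cumulative risk would understate the risk by that age. A yearly series built on rule B would also not end at the whole-period proportion defined in the same section, so two tables under one label would disagree.

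**Working it through.** **1. Can the two paragraphs be reconciled?** Let N be the starting cohort, d(j) the first events in year j, and D(k) = d(1) + … + d(k), with no censoring.

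- Rule A in year k: D(k) / N.
- Rule B denominator: that year's cases plus those with no outcome to date, d(k) + [N − D(k)] = N − D(k−1). Rule B in year k is therefore d(k) / [N − D(k−1)].

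If the rule B numerator were cumulative, its denominator would be D(k) + [N − D(k)] = N and the rules would coincide. The text rules this out, because it limits the numerator to the current year and removes earlier cases. In year 1, D(0) = 0 and the rules agree. After that, both numerator and denominator differ.

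**2. Inputs for the size.** The protocol states no yearly incidence, so there is no figure to reproduce. From the documents:

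- 4% NDD risk in the reference group (section 9.5)
- 12 years of follow-up in Denmark and Sweden, 10 in Norway (section 9.3.2.1)

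Assumed: no censoring, the 4% reached at the end of follow-up, and the shape of the hazard over age, for which the protocol gives no distribution.

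With S(k) the share event-free after year k, rule A = 1 − S(k) and rule B = 1 − S(k)/S(k−1). The total cumulative hazard is −ln(0.96) = 0.04082.

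**3. Constant hazard.**

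- Over 12 years, h = 0.04082/12 = 0.003402 per year, so rule B = 1 − exp(−0.003402) = 0.34% in every year.
- Over 10 years (Norway), h = 0.004082, so rule B = 0.41% in every year.

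| Setting | Year | Rule A | Rule B | A/B |
|---|---|---|---|---|
| Denmark, Sweden | 1 | 0.34% | 0.34% | 1.0 |
| Denmark, Sweden | 6 | 2.02% | 0.34% | 5.9 |
| Denmark, Sweden | 12 | 4.00% | 0.34% | 11.8 |
| Norway | 10 | 4.00% | 0.41% | 9.8 |

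**4. Other hazard shapes, 12 years.**

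- *Hazard rising linearly with age*, H(t) = 0.04082 × (t/12)². In year 5, rule A = 0.71% and rule B = 0.25%. In year 12, rule B = 1 − exp(−0.04082 × 23/144) = 0.65%, and 4.00/0.65 is about 6.
- *Hazard peaking in mid-childhood*, with assumed yearly weights 0.2, 0.5, 1, 2, 2, 2, 2, 2, 1.5, 1, 0.7, 0.5 (sum 15.4). In year 12, rule B = 1 − exp(−0.04082 × 0.5/15.4) = 0.13%, a ratio of about 30.

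**5. Does the gap carry into the meta-analysis?** Section 9.7.6 pools risk ratios between exposure groups, not absolute risks. Take 4% in the reference group and 8% in the valproate group (the doubling used in section 9.5), a constant hazard and year 12. Rule A gives 8/4 = 2.00. Under rule B the 8% group has 1 − exp(0.08338 × −1/12) = 0.692%, and 0.692/0.340 = 2.04. The two ratios differ by about 2%.

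**The case against.** The strongest defence is that the paragraph after the formula only defines the yearly count that is then summed, and that the defect is one badly worded denominator sentence. The stated reason for the fixed denominator, the formula and the whole-period definition all point to rule A, so the intent is recoverable. That last part stands, and it is why rule A should be the one kept. The reconciliation itself fails. As step 1 of the working shows, the second denominator returns the initial cohort only with a cumulative numerator, and the paragraph explicitly makes its numerator a single-year count.

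A reader might infer that separate programming in three countries will produce mixed definitions. The documents do not establish this. Section 9.6.2 says data are stored and analysed under local policy, but section 9.10.2 has a single contractor performing the study, including the analysis. Divergent programming is possible, not shown.

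A reader might also infer that pooling would blend risks that differ several-fold. Section 9.7.6 does not support that: it pools within-country risk ratios, in which the difference of scale largely cancels. Nor does it say that the yearly series, rather than the whole-period proportion, is what goes into the pooling.

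**Conclusion.** The contradiction is real and cannot be read away: one label covers a cumulative risk and a one-year conditional risk. Its reach is limited to the descriptive yearly absolute-risk series by exposure group. The whole-period proportion is clearly defined. The Cox HR and the logistic OR do not use the contested paragraph, and pooled risk ratios would move little.

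It is tempting to say that the reported yearly risks could be 12 times too small. That holds only for year 12, only in Denmark and Sweden, and only under an assumed constant hazard with no censoring. In year 1 there is no gap, and in Norway the constant-hazard maximum is about 10-fold, in year 10. For year 12 in the other two countries the factor is about 6 with a linearly rising hazard and about 30 with one that peaks in mid-childhood. The protocol gives no age pattern with which to choose among these. The sizes were worked out for NDD; for CM the same wording conflict applies, but no magnitude is claimed.

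**What to change.** Keep rule A: first events summed to date, divided by the cohort at the start of follow-up. It matches the formula and the whole-period proportion, so the yearly series will end at that figure. Then either delete the paragraph that follows the formula, or keep it for a separately named quantity, such as *annual incidence proportion among those still at risk*, and state that it is not reported or pooled as cumulative incidence. This costs an edit to section 9.7.2.2 and a check that any table shells use the same label. No new data are needed. If yearly tables have already been produced, confirm which rule was programmed and correct the label or the figures to match.
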